### 7.2 Statistical Methods

For Primary Aim (safety/feasibility) of *the main clinical trial*, all participants entering the psilocybin sessions (V3/3) will be included in the analysis of the safety profile and tolerability. Participants completing the two time points of pre- and post-treatment MRI and cognitive tests will be included in the analysis for the neuroscience objective. Participants who at least complete the follow-up at Week 1 (V6) will be included in the final analysis for the exploratory aim of clinical effects, regardless of whether they complete the full protocol. This approach is consistent with the intention-to-treat principle. A paired t-test will be used to investigate the pre- to post-treatment brain/cognitive metrics and symptom changes of *the main clinical trial*. Exploratory analyses will be performed to determine predictors of response including baseline individual features, using logistic regression. Safety profiles will be described by the percentage of each adverse effect.

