## **2.0 CLINICAL TRIAL OBJECTIVES**

### **2.1 Primary Objective of Main Clinical Trial**

To investigate the feasibility, tolerability, and safety of administering psilocybin in autistic adults with TRD.

Hypothesis 1a (feasibility): We will be able to recruit 20 participants within 21 months with retention >90%.

Hypothesis 1b (tolerability and safety): Adverse events (tolerability) and serious adverse events (safety) will be similar to those reported in the literature on classic serotonergic psychedelics in neurotypical populations.

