## **3.2 Primary Endpoints**

The primary safety endpoints of the main clinical trial design will be evaluated using standardized adverse events monitoring at all time points. Adverse event monitoring will be prioritized to closely and thoroughly evaluate the acute and sub-acute psychological safety profile. Blood pressure and heart rate will be examined before (V2) and during the psilocybin dosing sessions (V3/V4). Constant observation by therapists will monitor for adverse events during the dosing sessions. An on-call psychiatrist will be available at all times to further assess as needed for acute concerns. The safety endpoint is the number and severity of adverse events reported throughout the duration of the trial.

Feasibility endpoints of the main clinical trial design include the recruitment and retention rates. Dropout rates during three periods will be evaluated, namely: 1) screening period in which the participant undergoes medication tapering and washout; 2) during the acute course of the study intervention; and 3) during the follow-up after the intervention. Throughout all three periods, we will also evaluate adverse events including psychological distress and serious adverse events (e.g., hospitalization, suicide attempt, death).

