#### **4.7.3 Early Termination Visit**

If a participant withdraws from the clinical trial, every effort will be made to perform an Early Termination Visit.

Participants that withdraw after the first or second dosing session:

If the participant is willing to attend an Early Termination Visit, the following information will be documented:

- Assessment of new and ongoing AEs;
- Assessment of any complications following the study intervention;
- Documentation of all concomitant medications;

The PI will also ensure the participant is appropriately transitioned/followed for any additional care as required.

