## 7.0 STATISTICAL PLAN

### 7.1 Sample Size Determination

The proposed sample size of *the main clinical trial* is determined based on the recommendations for pilot trials (Whitehead et al., 2016) and is also a sample size adopted by earlier pilot trials on psilocybin (Carhart-Harris et al., 2016). For the main trial designed with 90% power and two-sided 5% significance, our sample size can detect an effect size (ES) of 0.76 (Cohen's d). We will be able to obtain reasonably reliable estimates on feasibility measures including recruitment (margin of error 15.5%) and retention rate (margin of error 13.1%) and tolerability (margin of error 10.1%). An fMRI study in healthy volunteers reports a very large psilocybin effect size in changes of functional connectivity at Week 1 (ES 1.73) (McCulloch et al., 2022). A meta-analysis of published psilocybin trials reports a large antidepressant effect size in neurotypical populations (ES 0.8) (Galvão-Coelho et al., 2021). Altogether, the proposed sample size of *the main clinical trial* appears to have sufficient power to detect the expected effects.

The proposed sample size of *the optional dense sampling brain MRI data collection* is determined based on a pilot study with the similar dense sampling neuroimaging approach happening at the CAMH (titled "Deriving Everyday Effects of Psychosis - Pilot (DEEP-Pi)"). The Midnight Scan Club dataset, representing the first multi-person deep phenotyping study in healthy individuals, also included a sample of 10 individuals, suggesting that for repeated scanning approaches a sample size of 10 is adequate (Gratton et al., 2018). Nonetheless, we acknowledge this rationale of the sample size decision is arbitrary and recognize this optional dense sampling approach is preliminary and novel.

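### The primary safety set leaves out harms of participants who taper but are never dosed, and a Week-1 completer set is labelled intention-to-treat

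*Protocol*

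**What the plan says.** Protocol section 7.2 fixes two analysis sets. For the primary aim, "all participants entering the psilocybin sessions (V3/3) will be included in the analysis of the safety profile and tolerability". For clinical effect, "Participants who at least complete the follow-up at Week 1 (V6) will be included in the final analysis for the exploratory aim of clinical effects", whether or not they finish the rest of the protocol. The next sentence reads "This approach is consistent with the intention-to-treat principle".

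Other sections bear on both sets:

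- **3.2** takes the number and severity of adverse events over the whole trial as the safety endpoint. It names three periods, the first being taper and washout, and adds: "Throughout all three periods, we will also evaluate adverse events including psychological distress and serious adverse events".
- **8.1** collects adverse events from V1 to V9, yet defines an adverse event as something that happens to a person given the investigational product.
- **8.5** withdraws at once anyone with a serious adverse event. **4.7.1** replaces withdrawn participants, aiming at 20 who complete. **4.7.2** ends data collection at withdrawal.
- **4.6** says that adverse events of screen failures will be used so that reporting is transparent.
- **4.7.3** lists the content of an Early Termination Visit for people who leave after a dose. It includes "Assessment of new and ongoing AEs", complications and medications, but no depression score.
- **6.1.2.1** collects the BDI-II at V5, one day after the 25 mg dose.

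**The concern.** The taper is imposed by the study, and section 1.6 names worsening of symptoms as one of its risks. Section 3.2 accordingly counts taper-phase events within the primary endpoint. An analysis set that starts at dosing cannot show the harms of people who taper and then drop out, so the primary safety result describes a narrower experience than the endpoint promises.

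For clinical effect, requiring a Week-1 assessment drops dosed participants who leave before it. If they tend to do worse, the remaining mean change is too favourable. Section 2.3 expects the antidepressant effect size to be close to the one reported in neurotypical depression, so an upward bias goes straight into that comparison. A reader told that the set follows intention-to-treat would not look for it.

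**Working it through.** **1. The plan's own figures.** Section 7.1 states: "For the main trial designed with 90% power and two-sided 5% significance", "our sample size can detect an effect size (ES) of 0.76 (Cohen's d". For a paired t-test with n = 20 (noncentral t, 19 degrees of freedom), d = 0.76 gives power 0.897, and 90% power needs d = 0.764. The stated retention margin of 13.1% also reproduces: 1.96 × √(0.90 × 0.10 / 20) = 0.1315. Both figures rest on n = 20 and are sound. The fault lies in who is counted, not in this arithmetic.

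**2. Safety: endpoint against analysis set.**

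| Participant | In the 3.2 endpoint and 8.1 collection window | In the 7.2 safety set |
|---|---|---|
| Taper event, later dosed | Yes | Yes: 7.2 selects people, not events |
| Non-serious taper event, leaves before V3 | Yes | No |
| Serious taper event | Yes | No: withdrawn under 8.5 before V3 |
| Meets the suicidality exclusion (4.4.2, criterion 11) by V2 | Yes | No: 4.1 requires eligibility at V1 and V2 |
| Serious event after dosing | Yes | Yes |

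Applied as written, 8.5 means that the 7.2 set can hold no taper-phase serious adverse event. A zero there would follow from the rule and would not be an observation.

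Section 4.6 closes the gap only in part. It gives no denominator and no place in the primary analysis, and it covers people who fail eligibility. Someone who leaves by choice during the taper, or between V2 and V3, is not clearly a screen failure. The visit content in 4.7.3 is listed only for those who leave after a dose. The definition in 8.1, read literally, does not even call a pre-dose event an adverse event.

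Illustration (assumed numbers; the protocol gives none): if 22 to 30 people start the taper and 1 or 2 leave before V3 with a serious event, the share harmed runs from 1/30 = 3.3% to 2/22 = 9.1%. The 7.2 set would show none of these events.

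**3. Clinical effect: size of the completer bias.** Let 20 participants complete V6 with mean change M. Let k further dosed participants leave before V6 with zero change (assumption), each replaced under 4.7.1.

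- Completer mean = M
- All-dosed mean = 20M / (20 + k)
- Ratio = (20 + k) / 20

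k = 1 gives 21/20 = 1.05; k = 2 gives 22/20 = 1.10.

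Section 2.1 expects: "We will be able to recruit 20 participants within 21 months with retention >90" per cent. Counted among the dosed, 20/22 = 90.9% meets that target and 20/23 = 87.0% does not, so k = 2 is the most that fits it. Without replacement the factor is 20/(20 − k): 1.05 for k = 1 and 1.11 for k = 2, nearly the same.

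On the standardised scale, take d = 0.80 in completers (the antidepressant effect size cited in 7.1) with SD 1, and p = 20/(20 + k). The all-dosed d is 0.8p / √(1.64p − 0.64p²).

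- k = 1: 0.762 / √0.981 = 0.77
- k = 2: 0.727 / √0.962 = 0.74

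**The case against.** The best defence of the safety set is that the primary objective in 2.1 is the safety of giving psilocybin, for which a dosed set is conventional, and that 8.2 has every event assessed for relatedness. Harms before dosing are still collected (8.1), evaluated (3.2) and, for screen failures, reported (4.6). This stands in part: a dosed set should be kept for drug-related events, and nothing suggests that taper harms would be concealed. It does not settle the matter, because the protocol's own endpoint also covers the taper and 7.2 gives those events no analysis.

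On clinical effect, the aim is exploratory, and 2.3 says that the trial is not powered for efficacy. The V5 score is no ready substitute, since 3.4 places symptom endpoints at V6 and V7, and someone who leaves between V3 and V5 has no scheduled post-dose BDI-II at all. These points lower the weight of this half but do not make the label right.

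A reader might infer more than the text supports:

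- **That all taper harms are dropped.** They are not; events in people later dosed stay in, since 7.2 restricts participants only.
- **That withdrawal symptoms and drug effects will be pooled.** Section 7.2 does not say so. Period tables and a treatment-emergent definition can be left to the SAP.
- **That about half of those under surveillance are lost.** The 15.5% recruitment margin fits 40 people at a proportion of 0.5, but the protocol does not say what such a denominator would be.
- **That the mean could be inflated by 25%.** That needs 4 of 20 dosed to leave unreplaced, against both 4.7.1 and the retention hypothesis.
- **That a particular repeated-measures model is required.** The choice of estimator belongs in the SAP.

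**Conclusion.** The point holds in two parts of unequal weight.

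*Safety (important).* Sections 3.2 and 8.1 on one side and 7.2 on the other contradict each other about people who taper and are never dosed. Their harms fall outside the primary safety analysis, including every taper-phase serious adverse event if 8.5 is applied as written. The number affected cannot be derived from the protocol; the 3.3% to 9.1% range is an illustration only. No view is taken here on the withdrawal rule itself.

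*Clinical effect (moderate).* A set that requires V6 is a Week-1 completer set, and the intention-to-treat sentence is wrong. The exclusion can depend on outcome: a dosed participant with a serious adverse event before V6 is withdrawn, stops contributing data and is replaced. The mean change is inflated by 5% for one leaver and 10% for two, assuming zero change in leavers and replacement to 20 completers. Leavers who improved would shrink the bias; leavers who worsened would enlarge it. It is unclear whether the sentence is also meant to cover the safety set.

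**What to change.** **(a) Safety.** In 7.2, summarise adverse and serious adverse events from V1 for all consented or tapering participants, by the three periods of 3.2, each with its own denominator. Beside this, keep a dosed set for events with onset or worsening after the V3 dose. Reconcile 3.2, 4.6, 7.2 and the definition and collection period in 8.1, and correct the visit reference V3/3.

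**(b) Clinical effect.** Either define the set as everyone dosed at V3, using all collected post-baseline scores with a stated missing-data method and V6 completers as a labelled sensitivity analysis; or call the set Week-1 completers, delete the intention-to-treat sentence, and report how many dosed participants were excluded and why.

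**(c) Optional.** Offer a BDI-II at the Early Termination Visit to those who agree. This first needs 4.7.2, which bars research evaluations after withdrawal, and 4.7.3 to be reconciled.

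The cost of (a) and (b) is protocol wording and a longer safety table. Events are already to be collected from V1, so no new visit or participant is needed. Item (c) adds one 21-item questionnaire. The change should be made before the data are analysed.

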## CLINICAL TRIAL SUMMARY

|  |  |
|--|--|
| Title   | Psilocybin for Treatment-Resistant Depression in Autism: a Pilot Trial with Pre-Post Brain and Cognitive Measurement to Understand Mechanisms  |
| Short Title                                     | PAT-DA   |
| Phase   | Phase I  |
| Methodology                                     | Open-label clinical trial  |
| Clinical trial Duration                         | 33 months to complete all recruitment, study procedures, and data analysis.  |
| Participating site(s)                           | Single-Center  |
| Objectives                                      | To assess the feasibility, tolerability, and efficacy of the use psilocybin alongside psilocybin-assisted therapy (PAT) in autistic adults with treatment-resistant depression (TRD). Furthermore, the use of neuroimaging to explore the mechanisms underpinning antidepressant effects of psilocybin.  |
| Number of Participants                          | Twenty (ten male & ten female) intellectually-able/speech-fluent autistic adults diagnosed with treatment-resistant depression   |
| Study Intervention Reference Therapy/Comparator | 2 doses of psilocybin in conjunction with psilocybin-assisted therapy (PAT), 1 st safety dose of 10mg, 2 nd treatment dose of 25mg   |
| Duration of Intervention                        | 2 dosing sessions 1 week apart, each about 6-8 hours duration  |
| Statistical Methodology                         | Characteristics of the trial cohort will be summarized by mean (SD), median (minimum, maximum). Summary raw scores will be presented at each assessment time both numerically and graphically. A paired t-test will be used to investigate the pre- to post-treatment brain/cognitive metrics and symptom changes. Exploratory analyses will be performed to determine predictors of response including baseline individual features, using logistic regression. Safety profiles will be described by the percentage of each adverse effect. |

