At Study Visits 3 & 4 (V3/V4), participants will receive oral doses of psilocybin (safety dose of 10 mg at V3, treatment dose of 25 mg at V4), to assess the tolerability and efficacy of psilocybin. These sessions will be held one week apart and will last 6 to 8 hours each. These sessions will take place in a pre-decorated treatment room at CAMH. The sessions will be set up and led by Co-Investigator [name]. Throughout the entire duration of the dosing sessions, participants will be monitored by a minimum of two trained therapists.

At the end of each session, participants will be evaluated for safety by a study psychiatrist before being discharged. Participants will also rate the 11-Dimension Altered States of Consciousness (11D-ASC) at the end of each dosing day when the subjective effects of psilocybin have subsided to a negligible level.

Visit 5 (V5) will be held one day after administration of the treatment dose (V4). During V5 the participants will complete post-treatment clinical and cognitive assessments, alongside the second and final MRI scans (*of the main clinical trial design*). Participants will also undergo a 1-hour integration therapy session to debrief their experiences the day before. Visit 6 (V6) will be held one week following the treatment dose (V4). During V6 a second 1-hour integration therapy session takes place and all post-treatment clinical assessments will be repeated. Subsequent clinical progress will be evaluated virtually at V7, V8, V9, which will respectively be held 2, 4, and 12 weeks following the treatment session (V4). From V7-V9 the cognitive tasks and MRI will not be done for *the main clinical trial design*. A study psychiatrist will be available to respond to any concerns about changes in mental/physical states throughout the study.

Figure 1. Schematic for the Main Clinical Trial Design

Optional Sub-Study of Dense Sampling Brain MRI Collection (Section 6.1.2.2 and 6.2.2)

10 participants out of 20 participants in the main clinical trial could opt to receive 8 additional brain MRI scans besides the MRI scans at V2 and V5 required in the main clinical trial. These 8 additional scans will be assessed at V1, in the middle of medication washout/tapering period, V3, V6, V7, V8, 8 weeks following the treatment dose (V4), and

V9, respectively. At each optional MRI visit, self-rated Beck Depression Inventory-II (BDI-II) and Autistic Burnout Survey Items (ABSI) will also be collected.

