### 3.4 Exploratory Endpoints

Exploratory endpoints of *the main clinical trial design* include 1) brain changes, 2) changes in cognitive performance, 3) symptoms associated with depression, 4) other behavioural/psychological symptoms/features which are theoretically associated with PAT and depression:

- 1) Changes in brain network interaction will be evaluated using MRI at V5
- 2) Cognitive performance associated with hopelessness will be evaluated at V5.
- 3) Symptoms associated with depression, including core depressive symptoms, rumination, anxiety, suicidality will be evaluated at V6 & V7.
- 4) Other behavioural/psychological symptoms/features, which theoretically are associated with PAT and depression, including autistic burnout, interoception, alexithymia, psychological inflexibility, resilience, and quality of life, will be evaluated at V6 & V7.

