#### **4.7.2 Follow-up for Withdrawn Participants**

If a participant withdraws consent, the information that was provided by the participant and recorded by the study team before they withdrew consent will not be destroyed. However, once withdrawn from the clinical trial, no further research procedures or evaluations will be performed, or additional research-specific data collected on the participant. Reasonable effort will be made to obtain permission to document the reason for withdrawal.

Withdrawn participants will be seen clinically by the study investigator to ensure a plan for continued care outside of the study is established. If the participant is interested in hearing about other treatment options, they may be offered a referral to the CBT group for depression and anxiety in autistic adults at CAMH and/or a consultation with a psychiatrist to discuss pharmacotherapy options.

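### Section 7.2 counts every Week-1 completer in the clinical-effects analysis, but its paired t-test cannot use them at any later visit they miss

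*Protocol*

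**What the plan says.** Section 7.2 defines the set for the exploratory clinical aim: "Participants who at least complete the follow-up at Week 1 (V6) will be included in the final analysis", "regardless of whether they complete the full protocol". It adds: "This approach is consistent with the intention-to-treat principle". The method for symptom change follows: "A paired t-test will be used to investigate the pre- to post-treatment brain/cognitive metrics and symptom changes". The Clinical Trial Summary repeats that test. Neither place names the post-treatment visit.

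On timing, Section 3.4 states: "Symptoms associated with depression, including core depressive symptoms, rumination, anxiety, suicidality will be evaluated at V6 & V7". It gives the same two visits for burnout, interoception, alexithymia, inflexibility, resilience and quality of life. The design overview in Section 3.1 goes further: "Subsequent clinical progress will be evaluated virtually at V7, V8, V9, which will respectively be held 2, 4, and 12 weeks following" the treatment session. For the individual visits the Summary promises description: "Summary raw scores will be presented at each assessment time both numerically and graphically".

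The visit outlines (6.1.2.1) and the schedule of events (6.2.1) show what is collected:

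| Scale | Visits from V2 on |
|---|---|
| BDI-II, ABSI, SBQ-ASC | V2, V5, V6, V7, V8, V9 |
| GRID-HAMD-17, CGI, ASA-A, SHAPS, RRS-10, INQ-15, ISQ-8, GAFS-8, CD-RISC 10, AAQ-II, CFI | V2, V6, V8, V9 |
| WHOQOL-4 | V2, V8, V9 |
| MRI, Go/No-Go task | V2, V5 |

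**The concern.** The inclusion rule and the test do not fit together after V6. Someone who gives a Week-1 score and then leaves belongs to the analysis set by rule, yet drops out of any paired test at a visit they miss. Their Week-1 score, which is informative about the missing later one, goes unused. Changes at different visits then come from different subsets of people.

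The protocol's own rules make later loss potentially informative. Disease progression is a listed reason for withdrawal (Section 4.7.1), and a serious adverse event leads to immediate withdrawal (Section 8.5). Section 4.7.2 says that "once withdrawn from the clinical trial, no further research procedures or evaluations will be performed". Withdrawn participants are replaced with the aim of 20 completers (Section 4.7.1), which restores the number but not the people lost. If those doing worse at Week 1 leave more often, a later mean change looks better than it was, and part of any apparent durability is selection.

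**Working it through.** **1. What the stated sample size assumes.** Section 7.1 gives 90% power, two-sided 5%, for d = 0.76. For a paired t-test, power = P(T > t(0.975, n−1)), with T noncentral t, n−1 degrees of freedom and noncentrality d√n. With n = 20 and d = 0.76, power is 89.7%, so the figure reproduces. It assumes 20 complete pairs.

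**2. Pairs at a later visit.** At V6 the set has no missing V6 visit by definition, so a V2–V6 test loses nobody who has both scores. Section 2.1 hypothesises retention above 90%. Of 20, 18 is exactly 90%, so at most one may be lost (1/20 = 5%). Power at d = 0.76 is then 87.9% (n = 19), and 85.9% at n = 18 or 81.1% at n = 16. The loss of power is minor; the question is selection.

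**3. Which named endpoints fall after V6.** Comparing Section 3.4 with the schedule:
- V7 is a named endpoint visit and comes after V6. Only BDI-II, ABSI and SBQ-ASC are collected there.
- Rumination, anxiety, alexithymia, interoception, inflexibility and resilience are assigned to V6 and V7, but none is scheduled at V7. After V6 they are scheduled only at V8 and V9.
- Quality of life is assigned to V6 and V7 and scheduled at neither. Any test of its change must use V8 or V9.

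**4. Size of the selection effect (all inputs assumed; the protocol gives none).** Simulated GRID-HAMD-17, N = 20, means 20/10/11/12 at V2/V6/V8/V9 (true Week-12 change −8), SDs between 4 and 7, post-visit correlations 0.65 to 0.75, and odds of leaving rising 2.7- to 4.5-fold per SD worse at Week 1:

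| Loss after V6 | Overstatement by completer paired mean | Likelihood-type estimate, bias |
|---|---|---|
| 5% | 0.12–0.21 points | under 0.03 |
| 10% | 0.30–0.34 | under 0.03 |
| 20% | 0.50–0.66 | under 0.03 |

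The standard error of the Week-12 change is about 1.6 to 1.7. With random loss neither estimate is biased.

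**5. Cross-check without simulation.** Let z be the standardised Week-1 score (higher is worse) and p the proportion lost. Overstatement ≈ [p/(1−p)] × mean z of leavers × (ρ·SD9 − ρ0·SD0). Here ρ is the V6–V9 correlation and ρ0 the V2–V6 correlation. With assumed ρ = 0.65, ρ0 = 0.4, SD9 = 7 and SD0 = 4, the last factor is 4.55 − 1.60 = 2.95. Integrating the logistic dropout model numerically gives the mean z of leavers, for the 2.7- and 4.5-fold odds:
- 5%: 0.895 and 1.232, so (0.05/0.95) × z × 2.95 = 0.14 and 0.19
- 10%: 0.817 and 1.095, so (0.10/0.90) × z × 2.95 = 0.27 and 0.36
- 20%: 0.693 and 0.906, so (0.20/0.80) × z × 2.95 = 0.51 and 0.67

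These agree with step 4. If the V2–V9 correlation is also 0.4, the standard error with 19 pairs is √[(16 + 49 − 2×0.4×4×7)/19] = √(42.6/19) = 1.50, slightly below the range quoted.

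**6. In proportion.** At 5% loss the largest simulated bias is 0.21/1.6 = 0.13 of a standard error, or 0.21/8 = 2.6% of the change. At 20% loss it is 0.66/1.6 = 0.41 of a standard error, or 8.3%.

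**The case against.** A reader might infer that the protocol fixes paired t-tests at Weeks 4 and 12 and so discards Week-1 completers there. The text does not support that. Section 7.2 names no visit, Section 3.4 places the symptom endpoints at V6 and V7, and for V8 and V9 the document promises evaluation and descriptive scores. A reader might also infer that the inclusion rule is never carried out. At V6 it is: a person who later skips V9 still counts in a V2–V6 test.

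It can further be said that visit selection and missing-data handling usually sit in a statistical analysis plan, which is not shown. That is right, and their absence is not the point here. The point is that the protocol has already fixed a test that does not match its own inclusion rule at any visit after V6.

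The strongest objection is size. The inputs are assumed, the bias at hypothesised retention is a small fraction of a standard error, the primary aims are feasibility, tolerability and safety, and Section 2.3 says the trial is not powered for antidepressant efficacy. All of this stands and lowers the priority. So does a technical caution: BDI-II has six occasions from V2, and an unstructured covariance would need 6×7/2 = 21 parameters from 20 people.

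**Conclusion.** The point holds in conditional form. If symptom change is tested at any visit after V6, the paired t-test uses only those observed there, and neither the inclusive rule nor the intention-to-treat statement carries over. This is not hypothetical, since V7 is a named endpoint visit and quality of life can only be tested at V8 or V9. The V6 result is unaffected.

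The bias depends on worse Week-1 scores predicting departure. Under the assumed inputs it is about 0.1 to 0.2 GRID-HAMD-17 points at 5% loss, 0.3 at 10% and 0.5 to 0.65 at 20%, against a change of 8 points. At the hypothesised retention it is unlikely to alter a conclusion. It deserves consideration because the remedy is cheap, not because the trial depends on it. Whether participants who leave before V6 should be in the set is a separate question.

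**What to change.** In Section 7.2 and the Clinical Trial Summary:

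1. Name the visits tested for each scale, and reconcile them with Section 3.4 and the schedule of events, including quality of life and the scales not collected at V7.
2. For scales with more than one post-treatment visit, estimate change from V2 with a 95% confidence interval at each named visit from one repeated-measures model using all available data, with visit as a factor and Kenward-Roger degrees of freedom. Use an unstructured covariance for the four-visit scales (4×5/2 = 10 parameters). For BDI-II and ABSI use a parsimonious structure that allows unequal variances, such as heterogeneous AR(1) or heterogeneous compound symmetry. SBQ-ASC has the same six visits and would need the same treatment.
3. Keep the paired t-test for the MRI and task data, which have only two occasions.

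The cost is a few sentences and slightly more analysis work, with no extra data or participants. The model relies on missing-at-random, which cannot be verified but is weaker than what the completer test needs.
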